6.2 Schedule of Evaluations

Table 6.2 below summarizes the timing and type of assessments/evaluations throughout the study.

Schedule of Assessments and Data Collection

	Screening	Baseline	0h	24h	48h	72h	24h post-last infusion (± 6h) and as needed	Day 7 or Discharge*	Day 30	Day 60 - Phone	Day 90	Day 180 - Phone	End of Study
		Prior to study drug start		± 6h	± 6h	± 6h		± 6h	± 7 days	± 7 days	± 7 days	± 7 days	
Screen Failure Log	X												
Inclusion/Exclusion Criteria	X												
Demographics & Medical History	X												
Informed Consent	X												
Subject Enrolment / Randomization		X											
Study Drug Administration			X	X	X	X							
Physical Examination	X			X	X	X	XX		X		X		
Visual & Auditory Assessment ^e	X			X	X	X	XX	X	X				
NIHSS	X	X		X	X	X	XX	X	X		X		

GCS	X	X		X	X	X	XX	X					
ICH Score	X												
mRS	X							X	X	X	X*	X	
MoCA								X	X		X		
SIS-16									X		X		
Vital Signs (BP & pulse) ⁵		X		X	X	X	XX	X					
Safety Monitoring			X	X	X	X							
Urinary Output				X	X	X							
Hematology	X						XX						
Serum Chemistry	X						XX						
Coagulation Parameters	X						XX						
Urine Analysis	X						XX						
Liver Function Tests	X						XX						
Kidney Function Tests	X						XX						
Serum albumin	X												
Pregnancy Test (women of childbearing potential)	X												
Blood sample for future research ^x		X					XX						
CT scan	X						XX						
Chest x-ray ⁹⁶	X						X						
Prior Medications	X												
Concomitant Medications			X	X	X	X		X	X	X	X		
Concomitant Non-Drug Therapies			X	X	X	X		X	X	X	X		
Adverse Events			X	X	X	X	X	X	X	X	X		
End of Study													X

⁵ Includes assessments for cataracts, visual loss or field cut, disturbed color of tinnitus – Should be performed, whenever possible in awake patients
* Day 7 or Discharge– whichever comes first
⁵ Vital signs (blood pressure and pulse) and neurological functions will be assessed at least once every 4h during intravenous drug infusion Laboratory tests may be performed outside the ±6h window, if it is a standard site procedure to perform laboratory tests⁶ at a specific time each day.
XX These assessments must be performed within 24±6h following completion of the last infusion of the study drug
^xWe plan to collect (bank) additional blood samples at baseline and after the last infusion to be stored and analyzed in the future from subjects providing informed consent.
• Post-treatment scan should be performed within 24±6 hours of the last infusion even if it is terminated before day-5 of treatment
⁹⁶ A telephone interview to obtain a score on mRS (the primary outcome measure) may be allowed on a case-by-case basis if the subject is unable to return for an in-person evaluation on day 90.
⁹⁶ Chest x-ray must be performed in any intubated patient if PaO₂/FiO₂ ratio is <300.

6.3 Blood Banking Repository Sub-Study

The main study provides an opportunity to “bank” blood samples from the participants for future innovative ICH research, particularly if the efforts to develop DFO as a therapy for ICH are successful. Future pharmacogenetic studies may be considered to help define other therapeutic targets and responders vs. non-responders to DFO therapy. We, therefore, plan to collect additional blood samples at baseline and after the last DFO infusion (approximately 30 ml) to be stored and analyzed in the future. Subjects’ participation in this blood-banking repository will be optional; they do not have to participate in the repository sub-study in order to participate initially or to continue their participation in the main study. The blood samples from all participating sites will be sent to the Beth Israel Deaconess Medical Center (The Coordinating Center) by overnight mail. All samples will be stripped of identifiers and randomly assigned a unique code number. The key linking code numbers and identifying information will be kept in a secure location accessible only to the principal investigator of the study or his designee, on a password protected network drive. All samples will be

stored at -80 degrees Celsius low-temperature, locked, freezer until final planned analyses are formulated and carried out. The samples will be stored indefinitely or until no more remains for genomic and protein research that can be performed at future dates.

The exact questions to be asked and tests to be done in the future are not fully identified at this stage. We tentatively plan to investigate the relationship between polymorphisms from a panel of genes encoding iron-handling proteins (which includes genes involved in both intra- and extra-cellular iron metabolism, such as ceruloplasmin, haptoglobin, hemopexin, transferrin receptor, ferritin heavy- and light-chain, and heme-oxygenase 1 and 2 genes) and PHE, outcome, and response to DFO therapy. Genotyping will be performed using high-throughput genome-wide SNP genotyping methods. Genotype results from DFO- and placebo-treated subjects will be examined for differences in allele frequency that may be associated with risk of malignant PHE progression or response to DFO therapy. Extracted DNA samples will be genotyped without knowledge of the treatment arm by chip-based methods utilizing mass spectrometry. The exact location of genotyping is undetermined at this point in time, although it is likely to be performed at the Broad Institute, given our ongoing collaboration in ICH Genome Wide Association Studies.

We plan to seek ancillary funding to support these additional analyses. Once funding is secured and the final analyses are formulated, we plan to seek an IRB approval for the specified analyses and use of the blood banking repository data.

7 ADVERSE EVENTS

7.1 DEFINITION OF ADVERSE EVENTS

Adverse events are any *untoward* medical occurrence whether or not they are considered related to the study drug. An adverse event can be any unfavorable and unintended symptom, sign, disease or clinically significant abnormal test result occurring during the study which were either not present at baseline, or if present, worsened during the study in terms of either severity or frequency. When evaluating possible adverse events, an assessment should be made regarding its seriousness, severity and temporal relationship to the administration of the study drug. An adverse event is considered serious if it is life-threatening, prolongs hospitalization, requires re-hospitalization, results in significant disability, leads to death, or requires medical or surgical intervention to prevent one of the other listed outcomes. An assessment should be made regarding the seriousness, severity and relationship to the administration of the study medication as well as to the ICH. The following factors should be considered when evaluating possible adverse events: 1) the temporal sequence from drug administration; 2) patient's response after drug discontinuation or re-introduction; and 3) severity of the event. The investigators, on the basis of their clinical judgment and guided by the following definitions, should determine the relationship of an adverse event to the study drug(s) as: definitely related, i.e. following in a reasonable temporal sequence, known to be a complication of DFO, and having no other explanation; probably related, i.e. following in a reasonable temporal sequence and not reasonably explained by the patient's clinical state or other therapies; possibly related, i.e. could have been explained by other therapies or patient's clinical state; or unlikely or not related. The severity of adverse events should be graded as mild, moderate, severe, life-threatening, or fatal.

All adverse events or complications will be entered into WebDCU™ and assigned to a system-organ class and preferred term using the MedDRA coding dictionary. Each subject must be monitored closely throughout his/her hospitalization for serious adverse events (SAEs). All adverse events (serious and non-serious) should be assessed until day-7 or discharge, whichever occurs earlier, and serious adverse events until day-90 or withdrawal of consent, whichever is earlier.

7.2 POTENTIAL COMPLICATIONS OF THE STUDY INTERVENTION

Aspects of the study that have potential for risks are blood withdrawals, CT scan imaging studies, and injections of the study medication(s). There are no additional risks for any of these procedures other than those present in any routine clinical situation, especially for blood draws and CT scans. Patients may experience some temporary discomfort, bruising, or, rarely, infection or the formation of a small clot or swelling at the site of the needle puncture in the process of drawing blood or starting the intravenous drip. The condition of ICH, in itself, carries a high risk for secondary complications including serious life-threatening adverse events, and even death, whether or not the active study drug (DFO) is used. Recent studies indicate that approximately 40% of patients with ICH have a serious adverse event during hospitalization, of which approximately 26% can be fatal [Haley, 2005; Mayer 2005; Mayer 2006; Lyden 2007].

DFO has been extensively used in clinical practice for more than 40 years, and is approved by the Federal Drug Administration for the treatment of acute iron intoxication and of chronic iron overload due to transfusion-dependent anemia. Safety studies indicate that it is relatively well tolerated. The adverse reactions observed with DFO have been previously detailed in section 2.2.2.

The most observed adverse events in our Phase I study in ICH patients were injection site reaction (irritation, pain, erythema, infiltration) and a modest decrease in blood pressure, which did not require any medical intervention. One subject developed visual hallucination during IV infusion of DFO. Almost all of these adverse events were mild, self-limited, did not require specific treatment, and resolved spontaneously. There were no deaths or serious adverse events related to DFO use. There were 2 cases of respiratory failure, both of which occurred in the 62mg/kg/day dose-tier. They were thought to be related to aspiration pneumonia, and unrelated to the study drug. However, a recent expert review found that one of these cases was an undiagnosed case of ARDS, and concurred that aspiration was a plausible explanation for it.

In the first part of phase II investigation of DFO in ICH (HI-DEF trial, where subjects were treated with a continuous infusion of DFO at 62 mg/kg/day for 5 consecutive days), 5 cases of ARDS were reported among the first 42 participants. A detailed expert review of reported cases of respiratory failure and pulmonary edema revealed 2 more cases of undiagnosed ARDS. Overall, 6/7 of the ARDS cases in HI-DEF were in the DFO treatment arm; 3 were fatal and the cause of death was ARDS-related in 2/3 cases. The expert who was blinded to treatment assignment identified a plausible cause for ARDS, other than the study drug or ICH itself, in 4/7 ARDS cases, while no other explanation, other than the study drug or ICH, was apparent for the remaining 3 cases. Although the overall rate of ARDS was in line with published reports in ICH patients [Elmer 2013], the imbalance in the frequency of ARDS between the DFO- and placebo-treated groups raised concerns that the pulmonary toxicity of the drug was likely. There were no other safety concerns. A MedWatch report was filed with the FDA and Health Canada for an AE of hypophosphatemia that was judged to be serious (potentially life-threatening), unexpected, and possibly related to the study drug. Overall, hypophosphatemia of varying severity was reported in 3 subjects in HI-DEF; 2 in DFO- and 1 in placebo-treated patients.

The effects of DFO on the fetus are unknown. It is also not known if DFO is excreted in human milk. Therefore, women who are pregnant and those who are breast-feeding will be excluded from this study. Those with child-bearing potential must have a negative pregnancy test before participating in the study.

7.3 PREVENTION AND MANAGEMENT OF ADVERSE EVENTS

Aseptic and sterile techniques should be used during blood draws, which should be performed by experienced phlebotomists. Application of warm compresses to the site of IV infusion throughout the infusion period is advised to minimize the potential for injection site irritation. In order to maximize safety during this study, we are using a slow infusion rate of < 7.5 mg/kg/hour and are limiting the maximal dose that any subject can receive to 6000 mg per day. The subjects must be carefully monitored throughout their participation in the study as detailed above. Any medical complications

should be managed as appropriate, according to the standard clinical practice at participating institutions. There is no specific antidote to DFO. General symptomatic and supportive measures should be applied.

Subjects should be admitted to the Neurological Intensive Care or Stroke Unit, undergo repeated clinical (neurological and general physical examinations) and laboratory evaluations at regular intervals throughout their participation in the study for safety monitoring, and receive standard medical management for ICH based on the American Stroke Association Guidelines [Morgenstern 2010]. Pertinent issues, including blood pressure management, are detailed in the appendix II and III. Laboratory studies that are abnormal or worsen from baseline should be repeated.

It is important that investigators ensure maintenance of intravascular volume prior to administration of the drug infusions, especially in hypovolemic patients, to minimize DFO-induced hypotension; and to carefully observe the subjects during the initial 30 minutes of the intravenous infusion for possible adverse effects, such as an allergic/anaphylactic reaction, arrhythmias, or hypotension. If there are no adverse effects, the infusion should continue. All patients should be kept hydrated and, if necessary, fluid support should be used to prevent or treat hypotension. In more severe cases, use of inotropic agents may be required.

The skin at the site of IV infusion must be carefully inspected periodically for signs of irritation, induration, or inflammation during physical examinations, coincident with the times of all assessments of vital signs, during the infusion of the drug and for 24 hours afterwards. Section 5.2 above details appropriate measures for management of local injection site reactions.

In order to minimize the potential pulmonary complications of the study drug, the investigators MUST follow the following guidelines by ARDSNet for management of intubated patients [<http://www.ardsnet.org/system/files/Ventilator%20Protocol%20Card.pdf>]- please refer to appendix VI: **Ventilator settings** – 1) Tidal volume (V_T) = ≤ 8 cc/kg PBW (predicted body weight); 2) Plateau Pressure (P_{plat}) < 30 cm H₂O; 3) Peak Pressure (P_{peak}) < 50 cm H₂O; and 4) Positive End-Expiratory Pressure (PEEP): at least 5 cm H₂O. Investigators MUST also implement a **Ventilator Associated Pneumonia prevention protocol** – 1) Head of bed elevation at least 30 degrees or greater; and 2) Regular chlorhexidine mouth wash and oral care. In addition, a conservative fluid management strategy that aims to minimize or eliminate positive fluid balance and cautions against indiscriminate use of blood transfusion unless hemoglobin concentration drops below 7 g/dL is recommended. All patients must be closely monitored for any signs or symptoms of respiratory compromise, including ARDS (based on Berlin criteria – see appendix VII). A confirmed diagnosis of ARDS should lead to premature discontinuation of the drug infusion. Appropriate treatment and monitoring, including the use of invasive mechanical ventilation, low tidal volume, permissive hypercapnea, or high PEEP, should proceed according to the standard clinical practice at each institution. In patients with respiratory failure, strategies that decrease oxygen utilization, such as antipyretics to control fever and sedatives to control agitation; and appropriate use of neuromuscular blockade when asynchrony with the ventilator persists despite adequate sedation are recommended.

Infections with *Yersinia enterocolitica* and *Y. pseudotuberculosis* have been reported in DFO-treated patients. Although these are unlikely to occur in patients without significant systemic iron overload, appropriate bacteriological tests should be performed, and suitable antibiotic coverage for *Yersinia* should be instituted if a patient in the study develops fever accompanied by acute enteritis, abdominal pain, or pharyngitis. Appropriate treatment and monitoring should proceed according to the standard clinical practice at each institution.

7.4 CRITERIA FOR INTERVENTION DISCONTINUATION

The investigators may terminate the study drug infusion if, in their judgment, its continued administration poses harm to the patient's medical condition. The only pre-established criteria for premature discontinuation of the study drug are: 1) severe allergic reaction or anaphylaxis; 2) worsening of renal functions, defined as serum creatinine >2 mg/dl on 2 repeated measures 8 hours apart; 3) development of ARDS based on Berlin criteria/definition (see appendix VII); or 4) if the patient or his proxy voluntarily withdraws consent. Subjects whose study drug is discontinued but who do not withdraw consent should still be followed for 180 days.

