4.2 Exclusion Criteria

- 1) Previous chelation therapy or known hypersensitivity to DFO products
- 2) Known severe iron deficiency anemia (defined as hemoglobin concentration < 7 g/dL or requiring blood transfusions)
- 3) Abnormal renal functions, defined as serum creatinine greater than 2 mg/dl
- 4) Planned surgical evacuation of ICH prior to administration of study drug (placement of a catheter for ventricular drainage is not a contraindication to enrollment)
- 5) Suspected secondary ICH related to tumour, ruptured aneurysm or arteriovenous malformation, hemorrhagic transformation of an ischemic infarct, or venous sinus thrombosis
- 6) Infratentorial hemorrhage
- 7) Irreversibly impaired brainstem function (bilateral fixed and dilated pupils and extensor motor posturing)
- 8) Complete unconsciousness, defined as a score of 3 on item 1a of the NIHSS (Responds only with reflex motor or autonomic effects or totally unresponsive, and flaccid)
- 9) Pre-existing disability, defined as pre-ICH mRS ≥ 2
- 10) Coagulopathy - defined as elevated aPTT or INR >1.3 upon presentation; concurrent use of direct thrombin inhibitors (such as dabigatran), direct factor Xa inhibitors (such as rivaroxaban or abixapan), or low-molecular-weight heparin
- 11) Patients with confirmed aspiration, pneumonia, or evident bilateral pulmonary infiltrates on chest x-ray or CT scan prior to enrollment
- 12) Patients with significant respiratory disease such as chronic obstructive pulmonary disease, pulmonary fibrosis, or any use (chronic or intermittent) of inhaled O₂ at home
- 13) FiO₂ >0.35 (>4 L/min) prior to enrollment
- 14) Sepsis (present source of infection \pm lactic acidosis defined as serum lactate >5 mmol/L and pH <7.35); Systemic Inflammatory Response Syndrome (defined as Temp >100.4 F or <96.8 F; Heart rate >90 ; Respiratory rate >20 or PaCO₂ <32 mmHg; WBC >12 , <4 K/uL, or $>10\%$ bands); or shock (SBP <90 mmHg) at presentation
- 15) The presence of 4 or more of the following risk modifiers for ARDS prior to enrollment:
 - a) Tachypnea (respiratory rate >30)
 - b) SpO₂ $<95\%$
 - c) Obesity, defined as Body Mass Index (BMI) >30
 - d) Acidosis (pH <7.35)
 - e) Hypoalbuminemia (albumin <3.5 g/dL)
 - f) Concurrent use of chemotherapy
- 16) Taking iron supplements containing ≥ 325 mg of ferrous iron, or prochlorperazine

- 17) Patients with heart failure taking > 500 mg of vitamin C daily
- 18) Known severe hearing loss

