5.2 SAFETY MONITORING DURING STUDY DRUG ADMINISTRATION

All patients will be closely monitored for safety and neurological function during the administration of the study drug, and for at least 24 hours after completion of the infusions, in Neurological Intensive or Stroke Care Unit(s), staffed by stroke-trained neurologists and nursing staff. Patients will be monitored for all adverse events from the time of study drug initiation until day-7 or discharge, whichever occurs first; and, all new SAEs will be monitored until day-90 or resolution of the SAE. Continuing SAEs beyond day-90 will be monitored until day-180.

The patients will be closely observed during the initial 30 minutes of the infusion for possible adverse effects, such as an allergic/anaphylactic reaction, symptomatic bradycardia or hypotension. If there are no adverse effects, the infusion will continue. If a patient's neurological status deteriorates during the infusion, the NIHSS score and GCS will be reassessed by a member of the stroke team/study staff. Significant neurological worsening will be defined as an increase in NIHSS score of ≥ 4 points or a decrease of ≥ 2 points in GCS, compared to pre-treatment baseline values, that cannot be explained by other causes. A change of this nature lasting >4 hours could lead to premature discontinuation of the drug infusion based on the judgment of the local primary investigator(s). Vital signs (blood pressure and pulse) and neurological functions will be assessed at least once every 4h during intravenous drug infusion. Daily urinary output checks will be carried out every day until the day following the last infusion. An unexplained drop of $>20\%$ in mean arterial pressure will trigger review by the treating physician to determine its cause and if medical intervention is required. Fluid support will be used to prevent or treat hypotension. In more severe cases, use of inotropic agents may be required.

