The skin at the infusion site will be examined at the same time points to assess for the presence and extent of local site reactions/irritation. If evidence of mild erythema/irritation or swelling emerges during the infusion, more frequent monitoring will be instituted depending on the severity and observed rate of change to ensure that the reaction does not progress further. The use of local anti-inflammatory agents may also be considered. In the event that local irritation continues to progress along with worsening edema, and development of pain or papular/vesicular eruption, the infusion will be terminated at that site and restarted in a different location. Close monitoring of the new infusion site, as well as the original site, will continue. If irritation develops at the new site or progresses at the original site, the infusion will be terminated and will not be re-started in this patient. In cases of an allergic reaction or anaphylaxis, the use of antihistamines and steroids is often sufficient; ACLS airway management may be required in severe cases. Appropriate treatment and monitoring will proceed according to the standard clinical practice at each institution until the reaction has resolved. Routine physical and neurological examinations will be carried out on a daily basis during the infusions, and the NIHSS and GCS scores will be determined. Safety laboratories (Hematology; Coagulation; Serum chemistry; Kidney and liver functions; and urine analysis) will be performed on the day following the last infusion of the study drug. Laboratory studies that are abnormal or worsen from baseline will be repeated. The frequency of subsequent evaluation of safety laboratories will be determined by the treating physician on a patient-by-patient case.

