Subjects who receive the study drug(s) will be evaluated daily for the first 3 days (during study drug infusion while in hospital) and on day-7 or discharge from the hospital, whichever occurs first. Clinic visits will take place on days 30 ± 7 and 90 ± 7 . Telephone interviews will be conducted on day 60 ± 7 and 180 ± 7 .

The following assessments should be performed **after each daily infusion** (every 24 ± 6 h) and through the day following completion of the last infusion: 1) General physical examination; 2) Visual and auditory assessments; 3) Neurological examination, including NIHSS and GCS; and 4) Vital signs, including blood pressure and heart rate. A repeat head CT scan and blood samples for hematology, serum chemistry, renal and hepatic function tests, coagulation studies, and urine analysis should be obtained within 24 ± 6 h following the last infusion of the study drug. Vital signs (blood pressure and pulse) and neurological functions should be assessed at least once every 4h during intravenous drug infusions. Daily urinary output checks should be carried out every day until the day following the last infusion. In addition, the following data must be checked at least once daily for all intubated patients (or more frequently in patients with changes in respiratory status requiring changes in ventilator settings and increased oxygen requirement) throughout day-7 or discharge and entered into Web-DCU™: 1) $\text{PaO}_2/\text{FiO}_2$ ratio; 2) Plateau and peak pressures; and 3) Chest X-ray results (when available). **A chest x-ray is required if the $\text{PaO}_2/\text{FiO}_2$ ratio is < 300 .**

On day-7 or Discharge (whichever comes first), the following assessments are done: mRS, NIHSS, GCS, MoCA and visual and auditory assessments.

During hospitalization, the NIHSS and GCS should be done any time a subject's neurological status deteriorates, or whenever the investigator believes it is prudent to do an assessment. Laboratory assessments beyond those required for the study should be done whenever clinically indicated.

The **Day-30 (± 7)** will be an in-person visit comprised of a general physical examination, visual and auditory assessments, review of SAEs, and assessments of NIHSS, SIS-16, MoCA and mRS.

The **Day-60 (± 7)** assessments, which will be completed via telephone, will be comprised of a functional assessment to obtain a score on mRS and query for SAEs.

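### The Section 7.4 renal stop needs two creatinine values, but none is scheduled from the first infusion until the day after the last, so scheduled data cannot trigger it while a dose remains

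*Protocol*

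**What the plan says.** Section 7.4 opens its list with "The only pre-established criteria for premature discontinuation of the study drug are". The renal item on that list is "worsening of renal functions, defined as serum creatinine >2 mg/dl on 2 repeated measures 8 hours apart". The same limit applies at entry, where Section 4.2 excludes "Abnormal renal functions, defined as serum creatinine greater than 2 mg/dl".

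Scheduled renal testing falls on either side of dosing:

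- **Before dosing.** Section 4.3.2 includes renal function in the screening tests. Section 6.1.1 adds a pre-treatment chemistry sample if one was not already taken on arrival.
- **After dosing.** Section 5.2 says of the safety laboratories: "Kidney and liver functions; and urine analysis) will be performed on the day following the last infusion of the study drug". Section 6.1.1 says "renal and hepatic function tests, coagulation studies, and urine analysis should be obtained within" 24±6 h of the last infusion. In Table 6.2 the row "Kidney Function Tests" is marked at screening and in the post-last-infusion column, and is empty at 0, 24, 48 and 72 h.

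The checks that Section 6.1.1 requires after each daily infusion are physical, visual and auditory, neurological, and vital signs. There is no blood test among them. Section 5.2 adds one renal check: "Daily urinary output checks will be carried out every day until the day following the last infusion".

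Other testing is left open. Section 6.1.1 says "Laboratory assessments beyond those required for the study should be done whenever clinically indicated". Sections 5.2 and 7.3 ask for out-of-range or worsening results to be repeated, without a time. Section 7.4 also lets the investigator stop the drug on judgment.

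**The concern.** A stopping criterion protects a subject only if the data it reads arrive while there is still drug to withhold. By using 2 mg/dl both to exclude patients and to stop treatment, the protocol treats that value as a safety limit during the three treatment days. It then schedules no creatinine on those days. Whether the stop works in a given subject depends on whether the site happens to draw chemistry, at more than 20 sites.

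At stake is the safety of individual subjects during dosing, and whether a stated rule is applied in the same way across sites. No statistical quantity in the trial is at stake.

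**Working it through.** The protocol gives no figure to reproduce, so the check is a timeline.

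**Inputs**

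- Dose: 32 mg/kg/day for 3 consecutive days, at no more than 7.5 mg/kg/h (Section 5.1).
- Criterion: two creatinine values above 2 mg/dl, 8 h apart (Section 7.4).
- Scheduled post-dose test: 24±6 h after the last infusion, that is 18 to 30 h (Section 6.1.1, Table 6.2).
- Assumption: infusions start at nominal 0, 24 and 48 h.

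**Step 1: can a pre-dose value count?** No. A value above 2 mg/dl excludes the patient (Section 4.2), so both qualifying values must come after entry.

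**Step 2: scheduled values during dosing.** The criterion needs 2. The schedule provides 0.

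**Step 3: earliest time the stop can be met on scheduled data.** Relative to the end of the last infusion:

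- first value: 18 to 30 h
- confirming value: 18 + 8 = 26 h to 30 + 8 = 38 h

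Because the test is tied to the last infusion, this holds at any infusion rate. Relative to the first dose:

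| Third infusion | Ends at | First scheduled value | Repeat 8 h later |
|---|---|---|---|
| Maximum rate, 32/7.5 = 4.27 h | 48 + 4.27 = 52.3 h | 70.3–82.3 h | 78.3–90.3 h |
| Spread over 24 h (assumption) | 72 h | 90–102 h | 98–110 h |

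**Step 4: drug that could be withheld.** The course is 3 × 32 = 96 mg/kg, before the 6000 mg daily cap. Scheduled data can withhold 0 of 96 mg/kg. If a rise were confirmed before infusion 2, 2 × 32 = 64 mg/kg could be withheld. If it were confirmed before infusion 3, 32 mg/kg could be. These last two figures describe a hypothetical subject and do not estimate harm.

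**Step 5: how often this might matter.** The documents give no rate. Section 2.2.2 reports no significant renal change in Phase I up to 62 mg/kg/day for 3 days (186 mg/kg). Section 2.2.3 reports no safety concern other than ARDS in HI-DEF at 62 mg/kg/day for 5 days (310 mg/kg). The present course is 96/186 = 52% and 96/310 = 31% of those doses, again before the cap. That points to a low frequency, but the evidence is thin. Phase I had 20 subjects, three of them at 32 mg/kg. Section 2.2.3 says further HI-DEF analyses were still to be done. Section 2.1.3.2 lists impaired renal function as a reaction whose frequency cannot be estimated.

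**The case against.** The strongest reply is that the criteria in Section 7.4 respond to events, and that a fixed draw is not how the protocol detects them. Even for ARDS, the main safety concern, the daily oxygenation ratio is required only in intubated patients and the chest x-ray only when that ratio is below 300. Other patients rely on clinical detection. The renal stop is backed by intensive or stroke unit care, daily urine output, clinically indicated tests and investigator judgment. Section 7.3 also speaks of laboratory evaluation at regular intervals. Under the instruction to repeat abnormal results, a subject who enters with a raised creatinine at or below 2 mg/dl could be retested during dosing, and that is the subject closest to the limit. The management appendices and the manual of procedures are not among the documents reviewed and may set routine chemistry.

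Much of this stands. A reader might infer that the stop is inoperative during dosing, or that no creatinine would be measured. The documents do not support either inference, because unscheduled values can trigger the rule and a site may well have them.

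The gap remains all the same. The repeat instruction has no time and, in Section 5.2, follows directly after the post-infusion laboratories. The sentence in Section 7.3 names no test and no time. Urine output cannot satisfy a criterion written in creatinine. ARDS has required monitoring of all patients during dosing and required measurements in those who are intubated. A creatinine limit is seen only if blood is drawn, and nothing in the schedule requires that.

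**Conclusion.** The point holds for scheduled data. No scheduled creatinine can trigger the renal stop while a dose remains, and the earliest scheduled confirmation is 26 h after the last infusion ends. That interval needs only the 18 h lower limit and the 8 h spacing. The times counted from the first dose also assume nominal 24 h dosing and the stated infusion lengths.

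The consequence is limited. The expected frequency is low, the number of subjects affected is unknown and none is claimed, and other routes to stopping exist. A reader might take the 64 or 32 mg/kg figures as a measure of excess exposure, but nothing in the protocol supports that. Sample size, alpha and the primary futility analysis do not change. This is an inexpensive improvement to the safety schedule.

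**What to change.** Add to Section 5.2, Section 6.1.1 and the kidney function row of Table 6.2:

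> Obtain a local serum creatinine after infusion 1 and after infusion 2 (routine-care chemistry is acceptable) and review the result before the next infusion starts. If it is above 2 mg/dl, repeat it 8 h later and do not start the next infusion until the repeat is available. Stop study drug if the repeat is still above 2 mg/dl (Section 7.4); otherwise proceed.

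The hold is needed because Table 6.2 places drug administration in columns with a ±6 h window. If infusion 2 is given at 18 h, even a sample drawn at 10 h has its repeat at 10 + 8 = 18 h, which leaves 0 h for the result.

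**Cost.** At most 2 × 294 = 588 local tests, fewer where routine chemistry already exists, plus repeats for values above 2 mg/dl. In the few subjects with a raised first value the next infusion may be delayed. There is no delay if the sample is drawn early enough. If it is drawn just before the infusion, the delay is 8 h plus laboratory turnaround. A first sample at 24 h gives a repeat at 32 h, beyond the 30 h end of the window, so the text should say that waiting for a repeat is not a deviation. The post-infusion tests are timed from the last infusion and move with it. The analysis does not change.
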